### 9.3 Secondary analyses

For all secondary endpoints, descriptive statistics will be calculated and presented at each time point of measurement for both treatment groups. For continuous secondary outcomes, this will include the mean, standard deviation, median, interquartile range, minimum, and maximum. For categorical or ordinal secondary outcomes, frequencies and percentages will be reported. These descriptive summaries will be presented in tabular format, and appropriate graphical representations, such as line plots for longitudinal data, bar charts, or box plots, will be utilized to visually depict trends, distributions, and differences between treatment arms across all assessment time points. For all secondary endpoints, analysis of

covariance (ANCOVA) models will be employed, analogous to the approach for the primary outcome. The choice of link function will be tailored to the specific nature of each outcome variable (e.g., linear for continuous outcomes, binary logistic for dichotomous outcomes, or ordinal for ordered categorical outcomes). In instances of repeated measures, mixed-effects regression models will be utilized, incorporating random intercepts for individual participants to account for within-subject correlation. Each model will include the respective baseline value of the endpoint, age at baseline, and treatment group as fixed effects. Effect estimates for the treatment variable, along with their 95% confidence intervals (CI), will be reported. All analyses will be conducted using the Full Analysis Set (FAS). Sensitivity analyses will be performed using the Per-Protocol Set (PPS), without imputation of missing values, to assess the robustness of the findings.

**Responder analysis:** Explorative analyses comparing responders and non-responders in both groups regarding PCS-associated signature at baseline: CD11c and IgM expression and an aCSM frequency. For this analysis a binary logistic regression model will be implemented with the responder (yes/no) variable as the dependent variable, the PCS-associated signature at baseline, the group and the interaction term between PCS-signature at baseline and group as independent variables.

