After the last IA cycle, a blood sample for immunoglobulin titers is collected, the peripheral venous access (or Shaldon catheter) is removed and patients are discharged from the hospital if the investigator has no concerns. At EOT visit, patients will also complete the Chalder Fatigue Scale (Chalder et al., 1993), Fluge Score (Fluge et al., 2011; Fluge et al., 2015), and PEM questionnaires. In addition, patients will be instructed how to complete all of the requested questionnaires at home at follow up time points. If the IA treatments are performed according to the planned schedule, the end of treatment visit (EOT) will take place on Day 10. However, the EOT visit may vary between Day 9 and 12. If treatment needs to be terminated, the EOT can occur as early as day 2. In such cases, all examinations originally scheduled for day 10 will be conducted on the corresponding day. In addition, two of the four follow-up visits scheduled at month 2 (Day 60) and month 6 (Day 180; EOS, End of Study visit) will take place at the neurological wards and outpatient clinics respectively. Patients will be asked to bring all requested questionnaires (including Chalder Fatigue Scale), which they completed at home, to both follow-up visits, where further assessments and laboratory tests will be conducted. An optional second cerebrospinal fluid sample may also be taken on Day 60. The remaining two follow-up visits, scheduled at month 1 (Day 30) and month 4 (Day 120), will be conducted via telephone. During these visits, patients will be asked about any adverse events (AEs), concomitant medications, and questionnaires.

Figure 1 Schematic illustration of the study design

[figure not shown]

Table 1: Schedule of Assessments

| Period/Visit name  | SCR               | BL  | Treatment period (inpatient) |                 |                 |                 |                 |                 |                 |                 |     | Follow-up |                   |                  | EOS                |                         |
|--|-------------------|------------------|------------------------------|-----------------|-----------------|-----------------|-----------------|-----------------|-----------------|-----------------|-----|-----------|-------------------|------------------|--------------------|-------------------------|

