### Clinical effectiveness related endpoints

- Chalder Fatigue Scale (Chalder et al., 1993) at End of Treatment (EOT) visit and at month 1, 4, and 6 after the completion of IA
- Post-COVID-19 Functional Status (PCFS) scale (Klok et al., 2020) at month 1, 2, 4, and 6 after IA completion (only in patients with PACS-CFS)
- the SF-36 physical domain (Ware & Sherbourne, 1992) at EOT visit and at month 1, 2, 4, and 6 after IA completion
- Fluge questionnaire (Fluge et al., 2011; Fluge et al., 2015) at month 1, 2, 4, and 6 after IA completion
- PEM frequency, strength and severity by PEM questionnaire (Cotler et al., 2018) at EOT visit and at month 1, 2, 4, and 6 after IA completion
- the Bell disabling scale (Bell, 1995) at EOT visit and at month 1, 2, 4, and 6 after IA completion
- the Compass-31 questionnaire (Sletten et al., 2012) at month 1, 2, 4, and 6 after IA completion
- Schellong Test (Fanciulli et al., 2019) at EOT visit and at month 2 and optional month 6 after IA completion
- hand grip strength test, at EOT and at month 2 and optional at month 6 after IA completion
- the 6 Minute Walking Test (6 MWT) ("ATS statement: guidelines for the six-minute walk test," 2002) at month 2 after IA completion
- optional neuropsychiatric assessment at month 2 after IA completion

- neurocognitive assessments (MoCA and SDMT) (Nasreddine et al., 2005) (Strober et al., 2020) at month 2 after IA completion
- quality of life (QoL) determined by the PROMIS questionnaire at month 1, 2, 4 and 6 after IA completion (Cella et al., 2019; Yang et al., 2019)
- PROMIS cognitive function short form 4a
- VLMT (verbal learning and memory test) (Helmstaedter et al., 2001)
- BVMT-R (brief visuospatial memory test revised) (Benedict, 1997)
- WAIS-IV (Wechsler adult intelligence scale) (Wechsler, 2008)
- TAP (Test of attentional performance) (Zimmermann & Fimm, 2004)
- LPS 50+ (Leistungsprüfungssystem (performance testing system) for 50 to 90 years old) (Sturm et al., 2015)
- TMT-A / B, Trail Making Test A / B (Reitan & Wolfson, 1993)
- RWT, Regensburger Wortflüssigkeits-Test (Regensburg Word Fluency Test) (Aschenbrenner et al., 2000)
- WST, Wortschatz-Test (Vocabulary test) (Schmidt & Metzler, 1992)

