## 11 Software

R (version 4.4.2 or later) will be used. For multiple imputation of missing values, the package mice will be used (van Buuren and Groothuis-Oudshoorn (2011)). For mixed models, the R package lme4 will be used (Bates et al. (2015)). For marginal mean estimates, the R package emmeans will be used (Lenth (2024)).

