**Table 14.2.4 Secondary endpoints (examples)**

| EORTC                        | Mean (95%CI)               |                       | Mean difference
(IG – KG)
(95% CI) | p-
values |
|------------------------------|----------------------------|-----------------------|--|--------------|
|                              | Intervention
group (IG) | Control group
(CG) |  |              |
| Chalder Fatigue score |                            |                       |  |              |
| EOT                          |                            |                       |  |              |
| 1 month                      |                            |                       |  |              |
| 4 months                     |                            |                       |  |              |
| 6 months                     |                            |                       |  |              |
| PCFS Scale            |                            |                       |  |              |
| 1 month                      |                            |                       |  |              |
| 2 months                     |                            |                       |  |              |
| 4 months                     |                            |                       |  |              |
| 6 months                     |                            |                       |  |              |
| SF 36 physical domain |                            |                       |  |              |
| 1 month                      |                            |                       |  |              |
| 2 months                     |                            |                       |  |              |
| 4 months                     |                            |                       |  |              |
| 6 months                     |                            |                       |  |              |
| ...                          |                            |                       |  |              |

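### Section 9.3 models repeated continuous secondary endpoints with a random intercept and no visit terms: it cannot supply the per-visit effects of shell 14.2.4, and adding visit terms alone would leave those intervals miscalibrated if adjusted spread differs between visits

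*SAP*

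**What the plan says.** Section 9.3 sets the model for repeated secondary endpoints: "In instances of repeated measures, mixed-effects regression models will be utilized, incorporating random intercepts for individual participants to account for within-subject correlation". It lists the covariates: "Each model will include the respective baseline value of the endpoint, age at baseline, and treatment group as fixed effects". The reported result follows: "Effect estimates for the treatment variable, along with their 95% confidence intervals (CI), will be reported". Section 11 names the software: "For mixed models, the R package lme4 will be used" and "For marginal mean estimates, the R package emmeans will be used".

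No random slope, visit-specific variance, robust standard error or sensitivity analysis of the covariance appears anywhere. The sensitivity analyses that are planned (sections 8, 9.2 and 9.3) change the analysis set or the imputation.

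Shell 14.2.4 has a mean difference with 95% CI on a separate row for each visit. Section 7.3 places the secondary Chalder assessments "at End of Treatment (EOT) visit and at month 1, 4, and 6 after the completion of IA", and under section 4 "the end of treatment visit (EOT) will take place on Day 10" if treatment runs to schedule; the last visit is Day 180. SF-36, PEM and Bell are also measured from end of treatment (EOT). Fluge, COMPASS-31 and PROMIS start at month 1.

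**The concern.** There are two linked gaps. First, with only baseline, age and group as fixed effects, the model has a single treatment coefficient, averaged over visits. It cannot give the visit-by-visit differences that shell 14.2.4 displays.

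Second, the natural repair (adding visit and treatment-by-visit terms) leaves a covariance that treats every visit as equally variable and every pair of visits as equally correlated. Day 10 and Day 30 would be taken to be as strongly correlated as Day 10 and Day 180. With complete data the model then uses one standard error at all visits. If patients differ more at one visit than another after baseline adjustment, some intervals are too wide and others too narrow.

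At stake are the error bars on the secondary estimates, including those at month 6.

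**Working it through.** **1. The plan's own precision figure.** Half-width = t(0.975; n1+n2−2) × 5.8 × √(1/n1 + 1/n2), with SD and group sizes from section 4.2.
- 44/22: 1.998 × 5.8 × 0.2611 = 3.03 (stated 3.03).
- 35/18: 2.008 × 1.682 = 3.377 (stated 3.37, truncated).

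Both reproduce. They use one SD; the SAP gives none by visit.

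**2. The model as listed.** Outcome = intercept + baseline + age + group + patient effect + residual. The variance is σu² + σe² at every visit, and the correlation is σu²/(σu² + σe²) for every pair. In simulation (400 trials per scenario, five visits, assumed AR(1) correlation 0.8), the averaged effect had coverage of 95.2% with flat SDs, 94.0% with SDs 4.6 to 6.9, 93.2% with 3.9 to 7.8, and 94.8% with 3.9 to 7.8 and 20% dropout. The Monte Carlo error is about 1 point. This model is adequately calibrated, but for a different quantity from that in the shell.

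**3. Visit and treatment-by-visit terms added.** With complete data the standard error at every visit is √(mean of the adjusted variances) × √(1/44 + 1/22). At visit j:
- ratio = √(mean variance) / SD_j
- coverage = 2Φ(1.96 × ratio) − 1

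SD_j is the SD left after baseline adjustment. Five visits with assumed, evenly stepped SDs give:

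| Adjusted SD, first to last | Model half-width | Needed, first / last | Coverage, first / last |
|---|---|---|---|
| 5.8 flat | 2.97 | 2.97 / 2.97 | 95% / 95% |
| 5.2 to 6.5 | 3.00 | 2.66 / 3.33 | 97.3% / 92.3% |
| 4.6 to 6.9 | 2.97 | 2.35 / 3.53 | 98.7% / 90.1% |
| 3.9 to 7.8 | 3.08 | 2.00 / 3.99 | 99.7% / 86.9% |
| 6.9 to 4.6 | 2.97 | 3.53 / 2.35 | 90.1% / 98.7% |

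Simulation agreed for the rows checked: 99.0% / 89.2% for 4.6 to 6.9, and 99.8% / 86.0% for 3.9 to 7.8.

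**4. Raw spread need not grow.** Keep the raw SD at 5.8 throughout and let the correlation r_j with baseline fall. With one common baseline slope b = mean of r_j:
- adjusted variance at visit j = 5.8² × (1 + b² − 2b·r_j)
- mean adjusted variance = 5.8² × (1 − b²)

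Example with assumed r = 0.75, 0.70, 0.63, 0.52, 0.42 at Days 10, 30, 60, 120, 180, so b = 0.604:
- pooled SD = 5.8 × √0.635 = 4.62
- EOT SD = 5.8 × √0.459 = 3.93; ratio 1.18; coverage about 98%
- month 6 SD = 5.8 × √0.857 = 5.37; ratio 0.86; coverage about 91%
- half-width 2.37 at every visit, against 2.01 needed at EOT and 2.75 at month 6

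Simulation with 4,000 trials per pattern (44/22, complete data; Monte Carlo error about 0.5 point at 90% coverage):

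| Correlation with baseline, EOT to month 6 | Coverage at EOT | Coverage at month 6 |
|---|---|---|
| 0.77 to 0.58 | 97.2% | 91.2% |
| 0.75 to 0.42 | 97.6% | 90.7% |
| 0.84 to 0.48 | 98.7% | 88.7% |

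Across a wider set of twelve assumed patterns, month 6 coverage ran from 83.8% to 91.6%.

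**The case against.** **The miscalibration belongs to a model that the SAP does not write down.** This stands as a limit: fitted literally, the listed model keeps 93 to 95% coverage. But it cannot produce the shell's rows, and repairing only its fixed effects brings the covariance problem in.

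**The per-visit rows might come from separate ANCOVAs.** Section 9.3 also says that secondary endpoints are analysed by ANCOVA like the primary outcome, and shell 14.2.4 is only an example. That reading is open, and visit-specific ANCOVAs would be free of this problem. The same section, however, assigns repeated measures to the mixed model, so the text needs settling.

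**Size and direction are assumed.** This stands. A reader might infer that late intervals are always too narrow; the documents do not support that, because a shrinking adjusted spread makes the early ones too narrow instead.

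**Three other stronger readings fail.**
- That lme4 forces this structure: it can fit random slopes, so the restriction lies in the wording of section 9.3.
- That the planned analysis misjudges whether the effect fades: the SAP plans no contrast between EOT and month 6.
- That all repeated endpoints span Day 10 to Day 180: only Chalder, SF-36, PEM and Bell do among the questionnaires. The Post-COVID scale is ordinal and falls outside this point.

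**The trial is labelled exploratory and reports SDs by visit and arm.** This lowers the severity. Visible SDs would warn a reader but would not correct the intervals.

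**Conclusion.** The point holds in limited form. For continuous repeated secondary endpoints, section 9.3 lists a model that gives one averaged effect, while shell 14.2.4 asks for effects by visit. With visit terms added, the random-intercept covariance gives correct per-visit intervals only if baseline-adjusted spread is about equal at all visits.

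Under a constant SD of 5.8 and correlation with baseline that weakens over time, coverage is about 97 to 99% at EOT and 89 to 92% at month 6 for the three patterns shown. For an assumed rise in adjusted SD of 25 to 50%, last-visit coverage is 92.3 to 90.1%. Equal adjusted spread gives 95% throughout, and shrinking spread reverses the pattern. All of this rests on assumed variances and correlations and, for these figures, on 44/22 patients with complete data.

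The primary Day 60 ANCOVA is unaffected. Severity is low to moderate.

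**What to change.** Amend sections 9.3 and 11 for continuous repeated endpoints:
- a repeated-measures model with visit as a factor, treatment-by-visit and baseline-by-visit terms, and age;
- an unstructured within-patient covariance, fitted for example with the R package mmrm or with nlme::gls;
- a prespecified fallback order if the fit does not converge: a simpler structure with visit-specific variances or visit-specific ANCOVA, then the random intercept;
- a statement that the rows of shell 14.2.4 are the visit-specific treatment differences from this model.

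Cost: a few sentences and one more R package. Five visits need 5 × 6 / 2 = 15 covariance parameters (10 for four visits), estimated from 66 patients, or 35 + 18 = 53 after the assumed dropout. The fit must also run in each of the 30 imputed data sets, so the fallback is a practical need.

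Late intervals get wider. In the three falling-correlation patterns, the month 6 SD with its own baseline slope is 5.8 × √(1 − r²), against a pooled 5.8 × √(1 − b²). With the correlation interpolated exponentially between the end values, this gives 4.72/4.20, 5.26/4.62 and 5.09/4.25, or 12%, 14% and 20% wider. EOT intervals get narrower.

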- IgM Expression: Mean fluorescence intensity (MFI) on total CD19 $^{+}$  B cells, Percentage of IgM $^{-}$  cells within the CD19 $^{+}$  gate, IgM MFI and %IgM $^{-}$  specifically on

IgDCD27+ memory B cells (CD19+IgDCD27+ gate), Activated Canonical Class-Switched Memory B Cells (aCSM), CD19+IgDIgMCD27+CD11c, Frequency quantification within total B cells or parent gates, Activated canonical class-switched memory B cells

Table 5: primary and secondary outcome variables

| Characteristic   | Variable            | Values   |
|--|---------------------|--|
| Primary outcome variable   |                     |  |
| Chalder Fatigue Scale at 2 months  | cfs_0001-cfs_0011   | 11 items with levels 0-3 each, sum score has to be calculated  |
| Secondary outcome variables  |                     |  |
| Efficacy related outcomes  |                     |  |
| Chalder Fatigue Scale at End of Treatment (EOT) visit and at month 1, 2, 4, and 6 after the completion of IA | cfs_0001-cfs_0011   | 11 items with levels 0-3 each, sum score has to be calculated  |
| Post-COVID-19 Functional Status (PCFS) scale   | pcfs_0020-pcfs_0050 | Ordinal scale, range 0 to 4 (0: no limitations, 4: severe limitations),  |
| SF-36 physical domain  | sf_0041-sf_0050     | 10 items, each scored with: no limitations (0 points), some limitations (5 points), severe limitations (10points), the sum will be calculated  |
| Fluge questionnaire  | ccc_0011-ccc_0131   | 5 domains with different number of items, domains: fatigue, pain, cognition, circulation, each item is scored from 0 to 10 according to the severity (10: highest severity), domains will be analyzed separately |
| Post-Exertional Malaise (PEM)  | pem_0021-pem_0110   | 11 items, 5 items scored 0 to 4 for frequency, 5 items scored 0 to 4 for severity, 1 item scored 0 to 6 for duration, sum score from 0 to 46   |
| Bell Score   | bell_0020           | 1 item with 11 statements, 0-100   |

|  |  |  |
|--|--|--|
|  |  | points (100: no symptoms, 0: severe symptoms)  |
| Compass-31   | com_0001-com_0031  | 31 items in 6 domains, score by domain are rescaled ranging from 0 to 100  |

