## 9.5 Planned subgroup analyses

For the statistical analyses of the subgroups, the models defined in the sections above will be used for the respective outcome, additionally with an interaction term of the treatment group variable with the subgroup, in order to obtain indications of differential treatment effects in the subgroups. We will report effect estimates of interaction effects with corresponding 95%CI. In addition, marginal effect estimates for each subgroup and 95% confidence intervals will be provided.

| Sub-group (levels)                     | Outcomes  |
|--|---|
| Sex (male, female, diverse)     | Primary endpoint and efficacy related secondary endpoints |
| Age
(< 40 years, ≥ 40 years) | Primary endpoint and efficacy related secondary endpoints |

| Sub-group (levels)  | Outcomes  |
|---|---|
| Education (higher education meaning A-levels or higher, medium or lower educational achievement)   | Primary endpoint and efficacy related secondary endpoints   |
| Employment status
(retired/ currently unable to work, employed/ self-employed endpoints / student)  | Primary endpoint and efficacy related secondary endpoints   |
| Body-mass index (BMI)
( $< 30 \text{ kg}^* \text{m}^{-2}$ , $\geq 30 \text{ kg}^* \text{m}^{-2}$ )  | Primary endpoint and efficacy related secondary endpoints   |
| ME/CFS vs. Post-COVID-ME/CFS   | Primary endpoint and efficacy related secondary endpoints, OCT outcome: Retinal vascular and perfusion density in the superficial vascular plexus (SVP) |
| Disease duration
( $\leq 2.5$ years, $> 2.5$ years)   | Primary endpoint and efficacy related secondary endpoints   |
| Bell Score at baseline
( $\leq 30$ , $> 30$ )   | Primary endpoint and efficacy related secondary endpoints   |
| Chalder Fatigue Scale at baseline
( $\leq 20$ , $> 20$ )  | Primary endpoint and efficacy related secondary endpoints   |
| Focal neurological deficit at baseline (yes, no)   | Primary endpoint and efficacy related secondary endpoints   |
| Antineuronal autoantibodies (yes, no)  | Primary endpoint and efficacy related secondary endpoints   |
| Subgroups by 7 PROMIS 29 sub domains (T-score cut offs of 30-40)   | Primary endpoint and efficacy related secondary endpoints   |
| Baseline detection of GPCR-Autoantibodies (pos. result from Labor Celltrend; yes, no)  | Primary endpoint and efficacy related secondary endpoints   |

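### The repeated-measures model in SAP Section 9.3 names no visit term, so as written it gives one time-averaged effect where the endpoints and Table 14.2.4 need one per visit

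*SAP*

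**What the plan says.** SAP Section 9.3 sets ANCOVA-type models for all secondary endpoints, by analogy with the primary analysis. It then adds: "In instances of repeated measures, mixed-effects regression models will be utilized, incorporating random intercepts for individual participants to account for within-subject correlation". On the terms in the models it says: "Each model will include the respective baseline value of the endpoint, age at baseline, and treatment group as fixed effects". On the output it says: "Effect estimates for the treatment variable, along with their 95% confidence intervals (CI), will be reported".

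Section 7.3 defines most clinical secondary endpoints by visit. The Chalder scale, for example, is listed "at End of Treatment (EOT) visit and at month 1, 4, and 6 after the completion of IA". Table 5 in the same section gives a different set of visits: "Chalder Fatigue Scale at End of Treatment (EOT) visit and at month 1, 2, 4, and 6 after the completion of IA".

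Table 14.2.4 has one row per visit for Chalder (EOT, 1, 4 and 6 months), PCFS and SF-36. Each row has group means, a mean difference with 95% CI and a p-value.

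Section 9.5 carries the models into the subgroup analyses, where "the models defined in the sections above will be used for the respective outcome", with a treatment-by-subgroup interaction added.

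**The concern.** A random-intercept model whose fixed effects are baseline, age and treatment has exactly one treatment parameter, an average over the visits included. The emmeans package named in Section 11 cannot recover visit-specific differences from a model that contains no visit. The stated model therefore cannot fill the table it is meant to fill.

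The reference to the primary approach allows a second reading, a separate ANCOVA at each visit, but the SAP does not say how that fits with the mixed model. The two readings give different estimates and different precision for every repeatedly measured secondary endpoint.

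The clinical question at stake is durability. After five treatments and follow-up to month 6, a pooled coefficient cannot separate an effect that fades from one that lasts. The same gap passes to Section 9.5, where a treatment-by-subgroup effect on these endpoints would also be a time average. With no visit main effect, common time trends also go into the residual. In the per-protocol sensitivity analysis, which uses no imputation, they could enter the treatment estimate if visits are missing unequally between arms.

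**Working it through.** **The SAP's own precision figure.** Section 4.2 gives half-widths of 3.03 points (44 vs 22) and 3.37 points (35 vs 18). With t(0.975, n1+n2−2) × 5.8 × √(1/n1 + 1/n2), these come out at 3.026 and 3.377, so they reproduce up to rounding. They concern the primary endpoint and are not in question. They supply the SD and group sizes used below.

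**Inputs.** From Section 4.2: 44 vs 22 patients and SD 5.8. From Section 7.3: four secondary Chalder visits (EOT, months 1, 4, 6). Assumed: equal correlation ρ = 0.5 between all visits including baseline (range 0.3 to 0.7), complete visits as after imputation, and the effect patterns below. Age is left out because it has no effect in the simulated data.

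**Standard errors.** √(1/44 + 1/22) = 0.261.

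- One visit, baseline-adjusted: 5.8 × √(1 − ρ²) × 0.261. At ρ = 0.5 this is 5.8 × 0.866 × 0.261 = 1.31.
- Average of m visits, baseline-adjusted: 5.8 × √[(1 + (m − 1)ρ)/m − ρ²] × 0.261. For m = 4 and ρ = 0.5, the bracket is 0.625 − 0.25 = 0.375, giving 5.8 × 0.612 × 0.261 = 0.93. For m = 5 it is 0.35, giving 0.90.
- Ratio: 1.31/0.93 = 1.4 (about 1.5 at ρ = 0.3 and 1.3 at ρ = 0.7).

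**What the pooled coefficient returns.** With complete visits and covariates that vary only between patients, the model without visit is equivalent to regressing each patient's mean score on baseline and arm. Three patterns of true Chalder reduction were simulated, 5,000 trials each:

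| True reduction at EOT / M1 / M4 / M6 | Mean | Pooled estimate (SE) |
|---|---|---|
| 3 / 3 / 3 / 3 | 12/4 = 3 | −3.0 (0.93) |
| 7 / 5 / 0 / 0 | 12/4 = 3 | −3.0 (0.93) |
| 0 / 0 / 6 / 6 | 12/4 = 3 | −3.0 (0.93) |

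Mixed models fitted directly in 150 replicates agree: −2.92 for the constant pattern and −3.01 for the fading one, SE 0.93.

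In the fading pattern, 3.0/0.93 ≈ 3.2, and the pooled 95% CI excludes zero in 88% of trials (88–95% over the correlation range). The true month-6 effect there is zero, so the same interval contains it in the remaining 12% (5–12%). Per-visit regressions recover −7.0, −5.0, 0.0 and 0.0 with SE 1.32 (1.09–1.45).

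**Independent illustration with five visits.** With assumed true effects of −1, −4, −4, −2 and 0 (mean −11/5 = −2.2), the model as written averaged −2.16 over 300 simulated trials. Adding visit and treatment-by-visit returned −0.95, −4.02, −3.96, −2.01 and +0.11.

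**Which visits enter.** For reductions of 2/4/6/2/0 at EOT and months 1, 2, 4 and 6, the average is 14/5 = 2.8 with month 2 and 8/4 = 2.0 without. The mismatch between Table 5 and the Section 7.3 list would therefore change a pooled Chalder estimate.

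**The case against.** The wording says that models will include three terms, not that they include only these. The sentence may simply list the covariates common to the linear, logistic, ordinal and mixed models. The visit-based endpoints, the visit-based table and the use of emmeans all suggest that visit-specific estimates are intended. Section 14.4 also plans a figure of effect estimates for the Chalder scale, which may be by visit; its content was lost in the PDF reading. This stands as evidence of intent, but it does not settle whether the estimates come from treatment-by-visit contrasts or from separate ANCOVAs.

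Table 14.2.4 is weak as a specification. It is labelled as examples, its header cell reads EORTC (an instrument not used in this trial), and its SF-36 rows omit EOT. The endpoints in Section 7.3 are nevertheless listed by visit regardless of the table. A time average is a legitimate summary, but the SAP would have to declare it as the target.

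The 88% and 12% depend on a chosen pattern. Its 7-point peak exceeds the 4.5-point difference cited in Section 4.2, and the 12% judges a time-average interval against a month-6 effect it does not target. These figures illustrate the problem; they do not predict an error in this trial.

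Treatment-by-visit models may be unstable for ordinal PCFS (post-COVID patients only) or binary POTS with at most 22 sham patients. That bears on the choice of remedy, not on the gap. The descriptive summaries by visit are pre-specified and would show a fading pattern, but without an adjusted difference or its interval.

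**Conclusion.** The concern holds. As written, the Section 9.3 model gives one time-averaged coefficient for each repeatedly measured secondary endpoint. That conflicts with the visit-based endpoints in Section 7.3 and the per-visit rows of Table 14.2.4, and the other plausible reading is not ruled in or out. Under the stated assumptions the pooled interval is about 1.4 times narrower than a visit-specific one and cannot distinguish a constant, a fading and a delayed effect with the same mean. The structural conclusion needs no simulation; only its size rests on the assumed correlation and effect patterns. It reaches the subgroup analyses of these endpoints through Section 9.5. It does not touch the primary day-60 ANCOVA or endpoints with a single post-baseline visit, such as the 6-minute walk, MoCA and SDMT. It should be fixed before the analysis.

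**What to change.** 1. In Section 9.3, for every endpoint with more than one post-baseline visit, state the fixed effects as baseline value, age, treatment, categorical visit and treatment-by-visit, with the participant random intercept. Report the adjusted treatment difference with 95% CI at each visit, and any overall average as an additional contrast.
2. Alternatively, state that a separate ANCOVA (or its logistic or ordinal counterpart) is fitted at each visit and drop the mixed model for these tables. This option also serves the sparse ordinal and binary endpoints.
3. State whether day 60 enters the Chalder mixed model, and align the Section 7.3 list, Table 5, Table 14.2.2 and Table 14.2.4. If it enters, label its estimate as supportive of the primary ANCOVA.
4. In Section 9.5, state the visit, or the average, at which each treatment-by-subgroup interaction is estimated.

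The cost is SAP wording and model code, with no change to design or data collection. For Chalder the mixed model gains 3 + 3 = 6 fixed-effect parameters with four visits or 4 + 4 = 8 with five, against 66 × 4 = 264 or 66 × 5 = 330 observations after imputation.
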